#### 2.0 STUDY OBJECTIVES

## 2.1 Primary Objective

- Phase 1 (Parts A and B): To assess safety and to identify the MTD, the RP2D, and the recommended dosing regimen of ASTX029.
- Phase 2: To assess preliminary clinical activity, as determined by ORR, in tumors characterized by gene aberrations in the MAPK signal pathway that may confer sensitivity to ASTX029.

## 2.2 Secondary Objectives

- To determine the PK profile of ASTX029 including the food effect on PK parameters.
- To evaluate other clinical activity parameters, such as duration of response (DOR), disease control rate (DCR), progression-free survival (PFS), and overall survival (OS).
- To evaluate relevant pharmacodynamic markers and target engagement (i.e., phosphorylated ribosomal s6 kinase [pRSK] inhibition) in tumor biopsies.

## 2.3 Exploratory Objectives

To identify and evaluate biomarkers of ASTX029 activity.

### 3.0 STUDY DESIGN

## 3.1 Overall Study Design

This is a first-in-human (FIH), open-label, multicenter, Phase 1-2 study to assess the safety of ASTX029, determine the MTD, RP2D, and recommended dosing regimen for ASTX029, and to obtain preliminary clinical activity, PK, and pharmacodynamic data in subjects with advanced solid tumors for whom standard life-prolonging measures or approved therapies are not available.

It is anticipated that up to 300 evaluable subjects will be enrolled in this study if the study fully enrolls both Phases 1 and 2. This includes approximately 120 subjects in Phase 1 at up to 14 study centers in the US and Europe and up to approximately 180 evaluable subjects in Phase 2 at up to 30 study centers in North America and Europe. The expected study duration is approximately 3.5 years (42 months), including approximately 36 months for recruitment and approximately 6 months for safety follow-up.

This study consists of 2 phases, as shown in the study schema below (Figure 1).

Phase 1 Part B Phase 1 Part A Phase 2 3+3 Dose Escalation Dose Expansion Regimen 1 (Continuous) NRAS-mutant melanoma Study Drug orally QD on Days 1-21 of each 21-day B. KRAS-mutant or KRAS-amplified NSCLC MTD/ C. BRAF V600-mutant cancers Initiate Regimen 2 Dose expansion in dose 10 mg 1 or more dose Regimen 2 (Intermittent) levels/regimens D. BRAF-fusion cancers Study Drug orally QD on BRAF- and RAS-Days 1-14 of each 21-day mutant cancers cycle E. Gynecologic cancers with alterations in the MAPK N=14 (per regimen MTD/ pathway RP2D and F. Tumors with other gene aberrations (HRAS GNAQ/GNA11, MEK) Optional Regimen 3 (Intermittent) N=10/19 (up to 29 total per cohort)

Figure 1: Study Schema

BRAF=B isoform of RAF kinase; FIH=first-in-human; MTD=maximum tolerated dose; RAS=rat sarcoma virus; QD=daily; RDE=recommended dose for expansion; RP2D=recommended Phase 2 dose.

Note: The RP2D and recommended dosing regimen will be used in Phase 2 as indicated by arrow.

The Phase 1 portion of the study consists of Parts A (Dose Escalation) and B (Dose Expansion). Part A is a dose-escalation stage to identify the MTD for up to 2 dosing regimens of ASTX029 and the recommended dose for expansion (RDE), defined as either the MTD or a dose below MTD that the Data and Safety Review Committee (DSRC) agrees shows adequate safety, PK, and/or preliminary biological or clinical activity. Subjects enrolled in Regimen 1 (continuous dosing)

receive ASTX029 orally once a day on Days 1 through 21 of each 21-day cycle. If Regimen 2 (intermittent dosing) is opened to enrollment, subjects enrolled in Regimen 2 will receive ASTX029 orally once a day on Days 1 through 14 of each 21-day cycle. Initially, subjects will be allocated to Regimen 1 (continuous dosing). The sponsor, with approval of the DSRC, will determine if Regimen 2 is to be opened for enrollment. Randomization to either Regimen 1 or Regimen 2 will begin if both regimens are open for enrollment. If the MTD is reached in 1 regimen before the other regimen, all subsequent subjects will be enrolled, without randomization, to the remaining regimen until the MTD is determined for each regimen evaluated.

The starting dose in Regimen 1 will be escalated stepwise in successive cohorts of at least 3 evaluable subjects each with additional allowed expansion to 6 subjects (3+3 study design) until the MTD is determined for the regimen. Dose levels and dosing regimens, the number of cohorts, and the number of subjects per cohort may be modified, as needed, in response to emerging data and recommendations from the DSRC.

Dose-escalation/de-escalation decisions will be based on the occurrence of dose-limiting toxicities (DLTs) during the first cycle of each dose level and the recommendations of the DSRC following review of all available safety, PK, and biomarker data from the completed first cycle of at least 3 subjects in each cohort. The DSRC RDE decision will be based on all available safety, PK, biomarkers, and preliminary activity data from all cycles (including potential for late or cumulative toxicity). The DSRC will also advise whether it is appropriate to proceed to Part B (Dose Expansion).

In Part B, one or more dose levels (and regimens) may be studied to supplement available safety, PK, and/or clinical activity data and to evaluate target engagement in firesh tumor tissue biopsies. A total of 14 evaluable subjects will be treated at each dose/regimen selected. If more than 1 dose/regimen is selected, subjects will be randomized in a 1:1 ratio. Subjects will have to meet the following molecular eligibility criteria: documented activating gene mutations in BRAF (BRAF V600 mutation or activating atypical non-V600 aberrations), Kirsten RAS (KRAS), NRAS, or Harvey RAS (HRAS). The RP2D decision by the DSRC will be based on all available PK, pharmacodynamic, safety, and preliminary activity data from all cycles (including the potential for late or cumulative toxicity). The RP2D could be the same or lower than the RDE.

The DSRC will advise when it is appropriate to proceed to Phase 2. The Phase 2 portion of the study will explore the preliminary single-agent antitumor activity of ASTX029 at the RP2D of the selected dosing regimen identified in Phase 1 Parts A and B in tumors characterized by gene aberrations in the MAPK signal pathway that may confer sensitivity to ASTX029. The Phase 2 part of the study will consist of the following 6 cohorts:

- Cohort A: NRAS-mutant melanoma.
- Cohort B: KRAS-mutant or KRAS-amplified non-small cell lung cancer (NSCLC).
- Cohort C: BRAF V600-mutant cancers (non-colorectal cancers).
- Cohort D: BRAF-fusion cancers.

- Cohort E: Gynecological cancers with alterations in the MAPK pathway.
- Cohort F: Tumors characterized by other gene aberrations that upregulate the MAPK signal pathway. In the Phase 2 part of the study, molecular eligibility will be based on the presence of documented gene aberrations in MAPK pathway.

For Phase 2, the sample size is based on a Simon's Optimal 2-stage design. Each cohort will enroll 10 subjects into the first stage of Simon's 2-stage design at the RP2D and the dosing regimen identified in Phase 1 Parts A and B. Should ≥2 first-stage subjects respond, an additional 19 subjects will be enrolled into the second stage. Therefore, up to 29 subjects will be enrolled into each cohort.

## 3.2 Study Endpoints

## 3.2.1 Primary Endpoint

- Phase 1: Incidences of DLTs and adverse events (AEs) to determine the MTD of up to 2 dosing regimens of ASTX029 and the RP2D and regimen to be taken to Phase 2.
- Phase 2: Clinical activity assessed by ORR according to RECIST v1.1 criteria.

## 3.2.2 Secondary Endpoints

- PK parameters of ASTX029, including area under the curve (AUC), maximum concentration (Cmax), minimum concentration (Cmin), time to reach maximum concentration (Tmax), elimination half-life (t½), food effect on ASTX029 PK parameters, and other secondary PK parameters of ASTX029 if data permit; analysis of ASTX029 metabolites if applicable.
- Inhibition of pRSK protein in response to ASTX029 treatment in tumor biopsies.
- Progression-free Survival (PFS).
- Overall Survival (OS).
- Disease Control Rate (DCR).
- Duration of Response (DOR).

#### 3.2.3 Exploratory Endpoints

- Suppression of mutant clones in circulating tumor DNA (ctDNA).
- Explore additional biomarkers of ASTX029 activity.

### 4.0 SAMPLE SIZE

The dose-escalation part of the study (Phase 1 Part A) follows a standard 3+3 study design, with a cohort size of 3 or 6 evaluable subjects. Dose escalation will continue until the MTD for each regimen evaluated is determined. Evaluable subjects for dose-escalation decisions in Part A are those who have completed the first cycle and have received at least 85% of planned doses in the first cycle of treatment (or were not able to receive at least 85% of planned doses due to safety concerns). The final sample size of part A will depend on the assessed dose levels and occurrence of dose limiting toxicities.

For Part B (of Phase 1), a sample size of 14 evaluable subjects will ensure a 90% probability of observing at least 1 adverse reaction to treatment for any adverse reaction with a  $\geq$ 15% incidence. Evaluable subjects for Part B are all subjects who receive any amount of study drug.

For Phase 2, the sample size is based on a Simon's Optimal 2-stage design (Simon 1989). Each cohort will enroll 10 subjects into the first stage. Should  $\geq 2$  first-stage subjects respond, an additional 19 subjects will be enrolled into the second stage. Therefore, up to 29 subjects will be used for each treatment cohort. The sample size, (10+19), or 29, under this Simon's Optimal 2-stage design, will achieve a power of 80% to test the null hypothesis of ORR p0  $\leq 0.1$  at a 1-sided alpha of 0.05 assuming the response rate p1 is 0.3. For Stage 2, the null hypothesis will be rejected if  $\geq 6$  responses are observed in a cohort of 29 subjects. For Cohort F (which will enroll patients with various tumor types and gene aberrations [Protocol Table 2]), the sponsor, with approval of the DSRC, may expand enrollment to 10 or 29 subjects for a particular molecularly defined subpopulation in which the most number of responses are observed, under the same Simon's Optimal 2-stage design as for the other cohorts for better assessment of activity in that disease subpopulation (Optional Cohort F expansion). It is expected that no more than 2 subpopulations will be expanded in this manner.

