The dose-escalation part of the study (Phase 1 Part A) follows a 3+3 study design, with a cohort size of either 3 or 6 evaluable subjects. Dose escalation will continue until an MTD is determined for each dosing regimen evaluated.

For Phase 1 Part B, a sample size of 14 evaluable subjects will ensure a 90% probability of observing at least 1 adverse reaction to treatment for any adverse reaction with a \geq 15% incidence. Evaluable subjects for Part B are all subjects who receive any amount of study drug.

For Phase 2, the sample size is based on a Simon's Optimal 2-stage design. Each cohort will enroll 10 subjects into the first stage. Should ≥ 2 first-stage subjects respond, an additional 19 subjects will be enrolled into the second stage. Therefore, up to 29 subjects will be used for each treatment cohort. The sample size, (10+19) 29, under this Simon's Optimal 2-stage design, will achieve a power of 80% to test the null hypothesis of ORRp₀ ≤ 0.1 at a 1-sided alpha of 0.05 assuming the response rate p₁ is 0.3. For Stage 2, the null hypothesis will be rejected if ≥ 6 responses are observed in a cohort of 29 subjects. For Phase 2 Cohort F (which will enroll patients with various tumor types and gene aberrations), the sponsor, with approval of the DSRC, may expand enrollment for a particular molecularly defined subpopulation in which the most number of responses are observed to 10 or 29 subjects under the same Simon's Optimal 2-stage design as for the other cohorts for better assessment of activity in that disease subgroup (Optional Cohort F Expansion). It is expected that no more than 2 subgroups will be expanded in this manner.

Efficacy:

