Note: Other gene aberrations that in the investigator's opinion may confer sensitivity to ASTX029 may be included in Cohort F after obtaining approval from the Sponsor's medical monitor.

For each potential subject, there is an up to 21-day screening and eligibility assessment period before enrollment; the first dose of study treatment will be administered on Cycle 1 Day 1 (C1D1). Subjects will continue to receive their assigned treatments throughout the study until the occurrence of disease progression, death, or unacceptable treatment-related toxicity; they elect to discontinue study treatment or withdraw consent to continue study participation; or until the study is closed by the sponsor.

Study visits will take place weekly during Cycles 1 and 2 and less frequently thereafter (see Table 11 and Table 12 for the complete schedules of events for the Regimen 1 and Regimen 2, respectively). Serial blood samples will be collected for PK and biomarker analyses at specified time points. If a formalin-fixed paraffin-embedded (FFPE) archived tumor biopsy is available, it will be obtained for use in this study during screening. In addition, in Phase 1 Part A and Phase 2, fresh tumor biopsies are optional during screening and posttreatment during Cycle 2. In

Phase 1 Part B, fresh tumor biopsies are mandatory during screening and posttreatment during Cycle 2.

Upon permanent discontinuation of study treatment, there is a Treatment Termination (Tx Term) visit and a 30-day (± 5 days or within 3 days before starting new treatment) Safety Follow-up visit. Subjects who remain on study after the 30-day Safety Follow-up visit will be contacted periodically by telephone for collection of long-term health status information.

Tolerability and safety of study treatment will be evaluated throughout the study by collection of clinical and laboratory data. Antitumor response will be assessed according to standard Response Evaluation Criteria in Solid Tumors (RECIST) v1.1 using computed tomography (CT) or magnetic resonance imaging (MRI) scans. Subjects whose disease is not measurable using RECIST v1.1 will be evaluated using another appropriate method.

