11.1. Sample Size

The dose-escalation part of the study (Phase 1 Part A) follows a standard 3+3 study design, with a cohort size of 3 or 6 evaluable subjects. Dose escalation will continue until the MTD for each regimen evaluated is determined. Evaluable subjects for dose-escalation decisions in Part A are those who have completed the first cycle and have received at least 85% of planned doses in the first cycle of treatment (or were not able to receive at least 85% of planned doses due to safety concerns).

For Part B (of Phase 1), a sample size of 14 evaluable subjects will ensure a 90% probability of observing at least 1 adverse reaction to treatment for any adverse reaction with a $\geq 15\%$ incidence. Evaluable subjects for Part B are all subjects who receive any amount of study drug.

For Phase 2, the sample size is based on a Simon's Optimal 2-stage design (Simon 1989). Each cohort will enroll 10 subjects into the first stage. Should ≥ 2 first-stage subjects respond, an additional 19 subjects will be enrolled into the second stage. Therefore, up to 29 subjects will be used for each treatment cohort. The sample size, (10+19) 29, under this Simon's Optimal 2-stage design, will achieve a power of 80% to test the null hypothesis of ORR $p_0 \leq 0.1$ at a 1-sided alpha of 0.05 assuming the response rate p_1 is 0.3. For Stage 2, the null hypothesis will be rejected if ≥ 6 responses are observed in a cohort of 29 subjects. For Cohort F (which will enroll patients with various tumor types and gene aberrations [Table 2]), the sponsor, with approval of the DSRC, may expand enrollment for a particular molecularly defined subpopulation in which the most number of responses are observed to 10 or 29 subjects under the same Simon's Optimal 2-stage design as for the other cohorts for better assessment of activity in that disease subpopulation (Optional Cohort F expansion). It is expected that no more than 2 subpopulations will be expanded in this manner.

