#### 7.0 STATISTICAL ANALYSIS

Unless otherwise specified, all statistical tests and confidence intervals (CIs) described in this document will be two-sided with alpha 0.05. Data summaries and listings will be generated using SAS version 9.4 or a more recent version (SAS Institute Inc., Cary, NC, USA).

The first dosing date is defined as the first date the subject received any study drug.

Analysis tables will be summarized by cohorts and all cohorts combined for phase 1 part A, phase 1 part B and phase 2 unless specified otherwise. For example,

- Phase 1A: Cohort 1, Cohort 2, ..., Cohort n
- Phase 1B powder in bottle and tablets
- Phase 2: Cohort A, Cohort B, ..., Cohort F
- Phase 1A, Phase 1B, and Phase 2

Tables may be combined and/or separated as allowed by number of cohorts.

The AEs will be summarized by assigned cohort at the onset of the AE (Section 7.6.2). Efficacy analyses, laboratory tests, vital signs, electrocardiogram (ECG), and Eastern Cooperative

Oncology Group (ECOG) performance status will be summarized by assigned cohort and all subjects combined (Total), unless otherwise specified.

The following will be summarized by assigned cohort and all subjects combined (Total), unless otherwise specified:

- · Efficacy analyses,
- Treatment emergent adverse events (TEAEs),
- · Laboratory tests,
- Vital signs,
- Electrocardiogram (ECG), and
- Eastern Cooperative Oncology Group (ECOG) performance status.

The following data listings by subject identification (ID) number (which includes the study center number) will be provided:

- All enrolled subjects
- Screen failure subjects (with reason for screen failure)
- Disposition (with reason(s) for discontinuation of treatment and withdrawal from study)
- Protocol deviations
- Demographic and baseline characteristics
- Study drug administration
- Individual efficacy data
- Subjects excluded from the efficacy analysis
- TEAEs
- Deaths (including primary cause of death)
- Serious adverse events (SAEs)
- Other significant TEAEs (including treatment discontinuation due to AEs)
- Concomitant medications

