## 7.5 Efficacy Variables and Analyses

Efficacy analyses will be based on the Efficacy Analysis Set (Section 5.3). Efficacy variables will be summarized using descriptive statistics. No comparison between treatment sequences will be performed.

Anti-tumor response is based on Response Evaluation Criteria in Solid Tumors (RECIST) v1.1 (Eisenhauer et al 2009). The details of RECIST v1.1 evaluation of responses can be found in protocol Appendix 3. The principal investigator assessment of RECIST v1.1 response will be analyzed.

Table 1 provides a summary of the overall response status calculation at each time point for subjects who have measurable disease at baseline. Details of complete response (CR), partial response (PR), progressive disease (PD), and stable disease (SD) assessments for Target and Nontarget Lesions are provided in Appendix 3 of the protocol.

Table 1: Summary of Overall Assessment of Response					
Time Point Response: Subjects with Target (±Nontarget) Disease					
Target Lesions	Nontarget Lesions	New Lesions	Overall		

Target Lesions	Nontarget Lesions	New Lesions	Overall Assessment of Response
CR	CR	No	CR
CR	Non-CR/Non-PD	No	PR
CR	Not evaluated	No	PR
PR	Non-PD or not all evaluated	No	PR
SD	Non-PD or not all evaluated	No	SD
Not all evaluated	Non-PD	No	NE
PD	Any	Yes or No	PD
Any	PD	Yes or No	PD
Any	Any	Yes	PD

CR=complete response, NE=inevaluable, PD=progressive disease, PR=partial response; SD=stable disease.

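### For a Cohort F subpopulation chosen because it has the most responses, the stated 1-sided alpha of 0.05 is not assured

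*SAP*

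**What the plan says.** Phase 2 uses one Simon rule. SAP 4.0 states that "Each cohort will enroll 10 subjects into the first stage"; a cohort continues with 19 more subjects at ≥2 responses, and the null is rejected at ≥6 of 29. The Protocol Synopsis gives the purpose: to "test the null hypothesis of ORRp₀ ≤ 0.1 at a 1-sided alpha of 0.05", with 80% power at a true ORR of 0.3.

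Cohort F mixes tumour types and gene aberrations. If the DSRC approves, the sponsor "may expand enrollment to 10 or 29 subjects for a particular molecularly defined subpopulation in which the most number of responses are observed" (SAP 4.0). The group is then assessed under the same Simon's "Optimal 2-stage design as for the other cohorts for better assessment of activity in that disease subpopulation". Protocol 11.1 has the matching text, "in which the most number of responses are observed to 10 or 29 subjects under the same" design. Both documents expect no more than two such expansions.

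Protocol Table 2 lists four kinds of aberration, but its note leaves the list open, subject to sign-off by the medical monitor: "Other gene aberrations that in the investigator's opinion may confer sensitivity to ASTX029 may be included in Cohort F after obtaining approval".

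The documents do not state:
- whether the responses that led to selection count towards ≥2/10 and ≥6/29;
- how many responses a group needs to be eligible;
- when the choice is made;
- whether Cohort F must itself have reached ≥2/10 first.

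The wording implies that the selecting responses count. Enrolment is expanded to 10 or 29, and where Protocol 4.1.2 uses the same verb for the other cohorts, 29 is explicitly a total.

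**The concern.** The 0.05 is a property of a rule applied to a cohort fixed before any outcome is seen. Here the group is chosen because its early outcomes were the best on view. If those outcomes are then counted, the same responses both nominate the group and help it over the boundary. No adjusted boundary is given, and the selecting subjects are not set aside.

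ORR is the Phase 2 primary endpoint. As written, an expanded subpopulation with ≥6/29 responses could be reported as having rejected ORR ≤ 10% at 1-sided 5%, with an observed ORR that overstates the true one.

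**Working it through.** **Inputs from the documents.** p0 = 0.10, p1 = 0.30, stage 1 n = 10 with continuation at ≥2, total n = 29 with rejection at ≥6, 1-sided alpha 0.05.

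**Assumptions, because the documents give no figures.** Four equally common groups, all true ORRs 0.10, selecting responses counted, ties broken at random, one expansion.

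**1. The plan's own figure.** Error = Σ over x ≥ 2 of P(X₁ = x) × P(X₂ ≥ 6 − x), with X₁ ~ Bin(10, 0.1) and X₂ ~ Bin(19, 0.1).

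- x = 2: 0.1937 × 0.1150 = 0.0223
- x = 3: 0.0574 × 0.2946 = 0.0169
- x = 4: 0.0112 × 0.5797 = 0.0065
- x = 5: 0.0015 × 0.8649 = 0.0013
- x ≥ 6: 0.0001

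The sum is 0.0471. The same sum at 0.3 gives 0.805. The stated alpha and power reproduce for a cohort fixed in advance.

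**2. What counting the selecting responses does.** A group holding m ≤ 10 subjects and y responses at selection rejects with probability Σₓ P(Bin(10 − m, 0.1) = x) × P(Bin(19, 0.1) ≥ 6 − y − x), over x with y + x ≥ 2. For m = 3 this is 0.095 when y = 1 and 0.259 when y = 2. Choosing the largest y puts the weight on such groups.

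**3. Overall error.** This is the probability that a group is selected and then falsely rejects. Selection after 10 was enumerated exactly; selection after 29 was simulated.

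| Responses needed in the group | Cohort F must have ≥2/10 | Selection after 10 | Selection after 29 |
|---|---|---|---|
| ≥1 | no | 0.076 | 0.117 to 0.120 |
| ≥1 | yes | 0.041 | 0.052 |
| ≥2 | yes | 0.025 | about 0.05 |

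The range in the first row reflects how stage 1 is applied to a group already holding more than 10 subjects, and simulation error. In the last row, the figure after 10 does not depend on the Cohort F requirement, because two responses in the group are two in Cohort F.

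*Sensitivity.* Leaving aside selection after 29 without the Cohort F requirement, 3 to 8 equal groups give 0.014 to 0.081, and a 50/25/15/10% split gives 0.029 to 0.073. For the case left aside, fixed splits of 29 subjects give 0.115 (10/10/9) to 0.129 (6/6/6/6/5).

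*Two expansions.* The reference without selection is 1 − (1 − 0.0471)² = 0.092. With ≥1 response needed, the overall rates are 0.094 (after 10, no requirement), 0.059 (after 10, requirement) and 0.066 (after 29, requirement).

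**4. Bias in the ORR.** If the group is filled to 29 regardless of stage 1, its expected ORR is (y + 0.1 × (29 − m))/29. With m = 3 this is (1 + 2.6)/29 = 12.4% for y = 1 and (2 + 2.6)/29 = 15.9% for y = 2, against 2.9/29 = 10% with no selection. Averaged over the selection process it is 12.9% (after 10, ≥1, no requirement), 14.6% (after 29, ≥1, requirement) and 15.8% (after 10, ≥2).

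**5. Error given expansion.** In the four-group cases these rates run from 0.117 to 0.255. They need their own reference. A cohort fixed in advance passes stage 1 with probability 0.264, so its error given ≥2/10 is already 0.0471/0.264 = 0.178. Its error is 0.113 given ≥1 response in its first 3 subjects, and 0.267 given ≥2 in its first 3.

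**The case against.** The strongest reply is that no overall failure of alpha is shown. Of the six results in the table, four are at or below about 0.05. The two clear excesses need a subpopulation to be opened without Cohort F first reaching ≥2/10, although SAP 4.0 applies stage 1 to every cohort. A Cohort F that reaches 29 under the plan has passed that stage. This stands. A reader might infer that the stated alpha fails outright, and the figures do not support that. They support only that the plan's text does not secure it.

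A reader might also set the error given expansion against 0.047 and conclude that it is several times too high. That comparison is wrong: any Simon cohort conditioned on early responses exceeds 0.047, as step 5 shows.

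A third tempting inference is that no output is planned for an expanded subpopulation, because SAP 7.0 shows "Phase 2: Cohort A, Cohort B, ..., Cohort F". That list is introduced as an example, SAP 7.0 allows tables to be separated, and SAP 1.0 places table specifications in another document. No omission can be concluded.

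It is fair to add that counting the selecting responses is implied, not stated. If only later subjects count, the error is 0.047 per expanded subpopulation. The expansion is also optional and exploratory in spirit, and SAP 7.5 says "Efficacy variables will be summarized using descriptive statistics". But that general sentence does not withdraw the rejection rule and alpha, which SAP 4.0 extends to the subpopulation by name of design.

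**Conclusion.** The concern holds in a limited form. The 1-sided 0.05 (exact 0.047) is derived for a cohort fixed in advance and is not assured for a Cohort F subpopulation picked for its responses, if those responses count. Under the stated assumptions with one expansion, the overall error runs from about 0.025 to about 0.12, and the outcome depends on rules the plan leaves open. It clearly exceeds 0.05 only where Cohort F need not first reach ≥2/10. No overall inflation is claimed for two expansions.

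The upward bias in the selected group's ORR is the more stable finding. It appears in every case examined where selecting responses count, at about 13% to 16% against a true 10%. Those figures ignore the stage 1 stop to isolate the effect of selection, so they are not the exact ORR the trial would report. All magnitudes rest on assumed group numbers and sizes.

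**What to change.** State in Protocol 11.1 and SAP 4.0 that the 1-sided alpha of 0.05 and the ≥6/29 rejection rule apply only to cohorts defined in advance. For a Cohort F subpopulation opened because of its responses, report the ORR with its exact 90% CI (the method already in SAP 7.5.1) as descriptive, once with and once without the subjects enrolled before selection. The cost is wording, one extra table and no formal claim for expanded subpopulations. No subjects are added.

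If the sponsor wants a test, base ≥2/10 and ≥6/29 only on subjects enrolled after selection, which gives 0.047 per expanded subpopulation. On average this adds about 3 subjects (selection after 10) or 8 (after 29) per expansion. It also lowers the chance of selecting and claiming a true 30% group among three 10% groups (≥1 response needed):
- after 10, no Cohort F requirement: 0.38 to 0.34;
- after 10, with the requirement: 0.23 to 0.20;
- after 29: 0.30 to 0.25.

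That choice is the sponsor's.
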